**6. \* Will individuals with limited English proficiency be included in or excluded from this research?**

- Included
- Excluded - safety concerns if participants are unable to communicate with the study team
- Excluded - instruments/measures only validated in English
- Excluded - no prospect of direct benefit to individual participants
- Excluded - minimal risk study
- Excluded - lack of budget/resources for translation and interpretation [provide an explanation in next question]
- Excluded - other reason [provide an explanation in next question]

**7. Justify the inclusion and exclusion criteria if you are either targeting, or excluding, a particular segment of the population / community. Provide a description of the group/organization/community and provide a rationale.**

We are excluding non-English speakers because:

1. There is insufficient budget to hire other language speakers.
2. The Muslim population is very diverse, and it isn't easy to include all languages.
3. Translating the study material and aims will affect the study quality.

## **PROMIS WOMAN Education Program : ImProving ceRvical cancer preventOn methods among Muslim Americans WOMEN**

### **Background, Rationale & Goals Section Complete**

Protocol Progress:

- **INITIAL SETUP**
- **BACKGROUND, RATIONALE & GOALS**
- ③ RESEARCH PLAN
- ④ CONSENT PLAN
- ⑤ RISKS, PRIVACY & CONFIDENTIALITY
- ⑥ POPULATIONS WITH SPECIAL CONSIDERATIONS
- ⑦ INSTITUTIONAL REQUIREMENTS
- ⑧ DOCUMENTS

Click Continue below to go to the next section

## PROMIS WOMAN Education Program : ImProving ceRvical cancer preventOn methods among Muslim Americans WOMEN

### Study Procedures

#### 1. \* Describe the study hypothesis and/or research questions. Use lay language whenever possible.

Aim 1b. We will conduct individual interviews with key stakeholders in our Community Advisory Board (Muslim religious leaders (N=4)) to receive feedback on the developed materials and inform the intervention program. This aim includes the Phase II (Preliminary Testing) of the ORBIT model (proof of concept, prepare the pilot).  
 Aim 2. We will test the preliminary efficacy of the religiously tailored and culturally appropriate intervention program. H1. Participants will show significant improvements in knowledge and acceptance of cervical cancer prevention after the intervention. To test this hypothesis, we will conduct a pre-post survey to examine changes in knowledge and acceptance of cervical cancer screening and prevention. This aim includes the Phase III (Efficacy) of the ORBIT model. Aim 3. We will test the feasibility and acceptability of the religiously tailored and culturally appropriate intervention program which includes education and experiential practice/communication skills training. We will recruit 20 participants with the same eligibility criteria as in Aim 1, who have not participated in our previous studies, and conduct a single-arm pilot trial. H2. We hypothesize that the religiously tailored and culturally appropriate intervention program will be feasible to conduct as evidenced by meeting enrollment targets and the ability to implement the program as planned. H3. The intervention will be acceptable as evidenced by engagement (>60%) and retention (>80%), and satisfaction survey ratings.

#### 2. \* Describe the study's specific aims or goals. Use lay language whenever possible.

Our team also investigates the barriers faced by MAW in the US healthcare system by evaluating the cultural competency of healthcare providers related to the Muslim culture at the VCU health system. Our ongoing work with the Muslim community has informed us about the community's needs. In this project, we will implement an intervention program guided by a community-based participatory approach utilizing expert-led education sessions and peer-led interventions, which combine health-related religious teachings and scientific information about the benefits of CC-S and HPV-Vax. The Muslim Community Partners (MCPs) will collaborate with our institute (VCU) by reaching out to four Islamic religious centers in Virginia. Partnership with Islamic centers is valuable to our project due to their: ability to convince women to join our study, reach out to a high number of MAW, and because religious voices will be a good motivator for Muslim families to change. The primary outcome is increasing awareness of cervical cancer prevention methods. The secondary outcome is the acceptability and confidence/trust in cervical cancer prevention methods such as CC-S and HPV Vax.

The research questions are: Would MAW intend to do cervical cancer screening and uptake the HPV Vaccination after an education program supported by the Mosques that they frequently visit?

The aims of the study are:

Aim 1b. We will conduct individual interviews with key stakeholders in our Community Advisory Board (Muslim religious leaders (N=4)) to receive feedback on the developed materials and inform the intervention program. This aim includes the Phase II (Preliminary Testing) of the ORBIT model (proof of concept, prepare the pilot).  
 Aim 2. We will test the preliminary efficacy of the religiously tailored and culturally appropriate intervention program.

H1. Participants will show significant improvements in knowledge and acceptance of cervical cancer prevention after the intervention. To test this hypothesis, we will conduct a pre-post survey to examine changes in knowledge and acceptance of cervical cancer screening and prevention. This aim includes the Phase III (Efficacy) of the ORBITT model. Aim 3. We will test the feasibility and acceptability of the religiously tailored and culturally appropriate intervention program which includes education and experiential practice/communication skills training. We will recruit 20 participants with the same eligibility criteria as in Aim 1, who have not participated in our previous studies, and conduct a single-arm pilot trial. H2. We hypothesize that the religiously tailored and culturally appropriate intervention program will be feasible to conduct as evidenced by meeting enrollment targets and the ability to implement the program as planned. H3. The intervention will be acceptable as evidenced by engagement (>60%) and retention (>80%), and satisfaction survey ratings.

For these aims, we will use a survey that includes:

Pre-test survey, the scales are:

1. Demographic
2. Perceived Discrimination
3. Religious Discrimination
4. Spiritual Health Locus of Control
5. Modesty
6. Cervical Cancer Knowledge
7. Perceived risk
8. Cuse of action
9. Self-efficacy
10. Attitude about CC screening
11. HPV vaccination acceptability

Post-test survey, the scales are:

2. Perceived Discrimination
3. Religious Discrimination
4. Spiritual Health Locus of Control
5. Modesty
6. Cervical Cancer Knowledge
7. Perceived risk
8. Cuse of action
9. Attitude about CC screening
10. HPV vaccination acceptability
11. General Self-Efficacy Scale (GSES)
12. Cervical Cancer Screening Self-Efficacy Scale

Satisfactory survey are:

- Experience with the intervention.
- Acceptability of content
- Acceptability of delivery

**3. \* Choose all types of recruitment materials that may be used and upload them below:**

- E-mail invitations
- Phone Solicitation scripts (i.e. cold calls or random-digit-dialing)
- Flyers, Mailed Letters or Newspaper/TV/Radio Ads**
- TeleGRAM announcements
- Website text
- Study-specific web sites (provide the design and text)
- Social Media
- EPIC MyChart Patient Portal research study descriptions
- Psychology Research Participant Pool (SONA) study descriptions
- Scripts for announcements made to groups
- Other recruitment document
- No recruitment materials

**4. \* Describe the study procedures/methods for identifying and recruiting participants. Address all of the following three aspects of recruitment in your response.**

- 1. Identification of potentially eligible participants or secondary data/specimens of interest.**
  - What database(s) will be queried to identify secondary data/specimens
  - How VCU Informatics or VCU IRDS will be used for cohort identification (when applicable, see help text)
  - How potential participants' contact information will be obtained
- 2. Recruitment procedures to invite participation in the study (when applicable):**
  - How each of the written or verbal recruitment materials and reminders (selected above) will be used
  - Who will contact, approach, or respond to potential participants
  - Locations where recruitment procedures will take place
  - The timing and frequency of recruitment attempts
- 3. Eligibility screening prior to consent and how those activities will be carried out (when applicable)**

**See the help text for additional guidance.**

The principal investigator (PI) has a community partnership with the Islamic Center of Richmond, where the research team will distribute flyers about the project (see attachment). The research team will be present at the Mosque at predetermined times where women could approach study team members to ask questions, sign up for participation, and schedule appointments.

1) Identification of potentially eligible participants:

- The research team will distribute flyers about the project at the Islamic Center of Richmond to identify potentially eligible participants.
- The education material will be mentioned as PDF in the docs section

2) Recruitment procedures to invite participation in the study:

Place: The research team will be present at the Mosque during predetermined times.

Participants: Women interested in participating can approach study team members to ask questions, sign up for participation, and schedule appointments.

Written recruitment materials, such as flyers, will be distributed to provide information about the study.

Verbal recruitment materials will be used when study team members interact with potential participants.

The research assistant will handle contact with potential participants, including scheduling interviews and baseline surveys.

Recruitment procedures will take place at the Islamic Center of Richmond.

3) Eligibility screening prior to consent and how those activities will be carried out:

During these interactions, eligibility screening will be conducted to ensure participants meet the study criteria.

The research team will use a standardized screening tool or questionnaire to assess eligibility.

For focus group meetings, participants will be screened for eligibility before being scheduled for interviews.

For the one-arm clinical trial, participants will be screened for eligibility during the scheduling of baseline surveys.

The education materials will be clearly outlined in the study plan PDF.

The survey will be given to the potential participants in person ( hard) or through QR code through redcap.

Summary the intervention :

The intervention group will consist of 20 participants who will receive one education session divided into three sections/videos. The session will be offered in a single day and last 1.5 hours. The session will include the following topics: 1) Risk of HPV infection (30 minutes), 2) Cervical cancer risk (30 minutes), and 3) Advantages and benefits of early screening and the HPV vaccine (30 minutes).

All participants from both groups will be given the survey at month 0 (baseline) after the delivery of the educational material. The survey will be self-report, available in both hard copy and electronic form with a QR code for Redcap.

Participants are expected to take approximately 45 minutes to complete the survey.

The Islamic center offer private room to practice the research activities in both phases ( Focus group and single arm trial)

**5. \* Does this study have a separate protocol document (i.e. a multisite or sponsor's protocol) that contains a detailed description of the study's methodology?**

Yes

No

**6. \* Since a separate protocol document is not uploaded, describe the proposed research using language understandable to those IRB committee members whose expertise is not scientific. The description must include:**

- 1. A statement explaining the study design**
- 2. A detailed description of all the procedures that will be followed to carry out the study, preferably in sequential order, and in sufficient detail that the study's methods could be replicated**
- 3. The schedule and frequency of when and how procedures will be conducted (e.g. in person, online, phone, paper, etc.)**
- 4. A description of all research measures/tests/interventions that will be used, including analyses/tests conducted on specimens/biological samples (if applicable)**

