**1. \* Describe the duration of the social/behavioral intervention, task, or environmental manipulation:**

The event will be organized for three hours.

-The education sessions will be 1.5 hours ( 90 minutes).

- The self-report survey will take 45 minutes.

- The rest of the time, we will have a break and lunch.

The education sessions will be offered on Saturday and Sunday.

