**4. If Other is selected, explain:****5. \* Select any waivers that apply to this consent / assent group:**

No Waivers Requested	
 Waiver of All Consent or Some Elements in Consent Form	
 Waiver of Parental Permission or Legally Authorized Representative Consent	
 Waiver of All Assent by Child or Decisionally Impaired Adult	
 Waiver of Signature on Consent/Permission Forms (waiver of documentation of consent)	
 Exception from Informed Consent (for emergency research only)	
6. * Select all study team role(s) that will obtain consent / assent from this group:	
Principal Investigator	
 Co/Sub-Investigator	
 Medical or Psychological Responsible Investigator	
Lead Student/Trainee Investigator (leading their own project)	
Research Coordinator	
 Research Nurse	
 Consultant	

Research Assistant	
Pharmacist	
Statistician	
Regulatory Coordinator	
Trainee/Student(working on project)	
Other	
N/A: Requesting Waiver of Consent	

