**When and Where Consent Will Occur:**

Consent for the intervention group will be obtained at the Islamic Center during the scheduled education sessions. Participants will have the opportunity to provide consent before engaging in the educational program.

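### The plan gives conflicting orders for consent, baseline survey and education session, so the baseline could be collected before signed consent or after the session

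*Combined protocol and SAP*

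**What the plan says.** All references are to the combined protocol and SAP.

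- **Study Procedures, question 4, item 3** covers what happens before consent. The form's own label is "Eligibility screening prior to consent and how those activities will be carried out". Under it the plan says "For the one-arm clinical trial, participants will be screened for eligibility during the scheduling of baseline surveys", and a few lines later "The survey will be given to the potential participants in person", with a REDCap QR code as the alternative to paper. The item names a separate screening instrument: "The research team will use a standardized screening tool or questionnaire to assess eligibility".
- **Study Procedures, question 4, summary of the intervention** says the month 0 baseline survey is given once the educational material has been delivered.
- **Study Procedures, question 6** lists enrolment of 20 women and then a baseline survey. Its schedule runs from brochure and screening to later enrolment, the consent process, and follow-up surveys by phone.
- **Behavioral Intervention/Task Details, question 1** sets a three-hour event with a 90-minute session. It adds "The self-report survey will take 45 minutes" and gives the remaining time to a break and lunch.
- **Consent Groups, intervention group, question 7** says "Consent for the intervention group will be obtained at the Islamic Center during the scheduled education sessions", before the woman takes part in the programme. The survey is not mentioned.
- **Same group, questions 8 and 10** select a mandatory period at home before signing and expect one to two weeks for the decision.
- **Same group, questions 2 and 5** require signed consent, with "No Waivers Requested".

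**The concern.** The design is a single-arm pre-post comparison, so the baseline survey is half of every efficacy contrast. Two things must be true of it: the woman has signed before she answers, and she answers before she is taught. The plan guarantees neither.

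The pre-test covers perceived and religious discrimination, spiritual health locus of control and modesty, and the plan proposes self-reported Pap smear and HPV vaccine history as well. Answers given before signature would breach the plan's own signed-consent requirement. Answers given after the session would already contain what the session taught. A later survey compared with them would then tend to understate any change in knowledge or attitude. Neither fault can be repaired once a woman has answered.

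**Working it through.** The plan states no figure on this point, so there is none to reproduce. The check sets the timing statements side by side and adds a time budget for the event.

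**Time budget.** Inputs from Behavioral Intervention/Task Details, question 1: event 3 h = 180 min, session 90 min, survey 45 min. For *k* surveys done on the day:

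remaining = 180 − 90 − 45*k*

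- *k* = 1: 180 − 90 − 45 = 45 min, which the plan gives to break and lunch.
- *k* = 2: 180 − 90 − 90 = 0 min for break, lunch, any consent discussion and the satisfaction survey.

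The timetable as written therefore fits one survey, and no consent slot is listed. The survey lists in Study Procedures, question 2, and the payments under Compensation confirm that each woman completes both a pre- and a post-survey.

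**What each reading implies.**

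| Reading | Source | Consequence |
|---|---|---|
| Survey goes to potential participants at screening | Question 4, item 3, with consent question 7 | Pre-test can be answered before signature |
| Event survey is the post-test | Task Details question 1, with the intervention summary's after-education timing | Pre-test falls before the event, so before consent as question 7 places it |
| Baseline follows the education | Question 4, intervention summary, taken literally | There is no pre-intervention measurement |
| Event survey is the pre-test and the post-test is by phone | Question 6, with Task Details question 1 | Compliant, provided signature comes first that day |
| Both surveys at the event | Task Details question 1 | 0 minutes left |

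Only the fourth row gives a workable order that is sound on both counts. No section selects it, and the intervention summary contradicts it.

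**Consent timing.** Question 7 obtains consent at a one-day session. Questions 8 and 10 send the woman home first, typically for one to two weeks. These fit together only if the consent discussion takes place at an earlier visit, which the plan does not describe. During such a wait, a woman already given the paper form or QR code could complete the survey unsigned. Nothing says that the code is specific to a participant or inactive until signature.

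**The case against.** The strongest reply is that the survey sentence in question 4 describes how the survey is delivered, not when. It carries no timing, it follows an unrelated line on education materials, and the intervention summary repeats the same paper-or-QR content as a statement of mode. Scheduling a survey is also not administering it: "participants will be screened for eligibility during the scheduling of baseline surveys" says only when eligibility is checked. Question 6 places enrolment ahead of the baseline survey. The signed-consent rule with no waiver suggests that research data follow signature. The zero-minute result assumes both surveys on the day, whereas question 6 puts follow-up surveys on the phone. The intervention consent form, the research assistant's communication script and the timeline are listed as uploads but were not available for this review. They may state the order.

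Most of this stands. A reader might infer that women will in fact complete the survey at screening, that all 20 baselines are at risk, or that the data will be unusable. The documents do not support any of these. No text places completion at screening, no number follows from what is written, and nothing says what happens to data obtained before consent. Nor is it shown that entries from women who never enrol would mix with the trial data. Active Internet Data Collection, questions 2 and 3, assigns study IDs and lists identity verification and screening questions, although the fraud checks are worded as possibilities.

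The reply does not remove the contradiction. A compliant reading exists, but staff could follow other sections of the same document and arrive at a pre-consent or post-education baseline.

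**Conclusion.** The point holds as a contradiction about sequence. Across Study Procedures questions 4 and 6, Task Details question 1, and intervention consent questions 7, 8 and 10, the order of consent, baseline survey and education is not consistent. No section requires signature before the pre-test or the pre-test before the session.

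The only computable size is the event budget: 45 minutes left with one survey and 0 with two. The number of women affected, and any resulting loss of baseline data, cannot be derived. The conclusion assumes that the uploaded documents not available here do not already settle the order. If they do, the protocol text still has to be brought into line with them.

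**What to change.** Reconcile the sections named above to one sequence:

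1. Before consent, the eligibility screener only.
2. Wait period.
3. Signed consent.
4. Pre-test released, on paper or by a participant-specific REDCap link, only after the signature is recorded.
5. Pre-test closed before that woman's session starts.
6. Education session.
7. Post-test.

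Specific edits:

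- **Study Procedures, question 4, item 3:** change *potential participants* to *consented participants* in the survey sentence.
- **Study Procedures, question 4, intervention summary:** remove the statement that the baseline survey follows the education.
- **Study Procedures, question 6:** state that the baseline survey follows signature.
- **Task Details, question 1:** say which survey the 45 minutes covers and where consent and the other surveys take place.
- **Consent Groups, intervention group, questions 7, 8 and 10:** say that consent precedes the pre-test as well as the programme, and how the wait at home fits with the place and time of signing.

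The cost is protocol wording and a REDCap setting; DocuSign and REDCap are already in the plan. The downside is that consent becomes tied to the baseline contact.

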In summary, hesitancy in cancer screening may explain, in part, the notable disparities in stage at diagnosis of cervical cancer observed among Muslim women. To date, the few studies aimed at determining factors contributing to the lack of cancer screening participation among Muslim women have not thoroughly investigated the social, behavioral, cultural, and systems-level factors contributing to disparities. Muslim women are characterized by a unique set of characteristics and cultures; thus, it is essential to understand how these factors contribute to the acceptance of the prevention and screening process. The sequential studies proposed herein aim at informing the science of cervical cancer prevention among Muslim women by using a theory-driven framework using a two-arms study design to improve the cervical cancer disparities among Muslim women.

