**2. \* Describe the study hypothesis and/or research questions. Use lay language whenever possible.**

Aim 1b. We will conduct individual interviews with key stakeholders in our Community Advisory Board (Muslim religious leaders (N=4)) to receive feedback on the developed materials and inform the intervention program. This aim includes the Phase II (Preliminary Testing) of the ORBIT model (proof of concept, prepare the pilot).  
 Aim 2. We will test the preliminary efficacy of the religiously tailored and culturally appropriate intervention program. H1. Participants will show significant improvements in knowledge and acceptance of cervical cancer prevention after the intervention. To test this hypothesis, we will conduct a pre-post survey to examine changes in knowledge and acceptance of cervical cancer screening and prevention. This aim includes the Phase II (Efficacy) of the ORBIT model.  
 Aim 3. We will test the feasibility and acceptability of the religiously tailored and culturally appropriate intervention program which includes education and experiential practice/communication skills training. We will recruit 20 participants with the same eligibility criteria as in Aim 1, who have not participated in our previous studies, and conduct a single-arm pilot trial. H2. We hypothesize that the religiously tailored and culturally appropriate intervention program will be feasible to conduct as evidenced by meeting enrollment targets and the ability to implement the program as planned. H3. The intervention will be acceptable as evidenced by engagement (>60%) and retention (>80%), and satisfaction survey ratings.

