**2. If this is a multi-Center Project, what is the maximum anticipated number of subjects across all sites?**

**3. Provide justification for the sample size by explaining how you arrived at the expected number of participants and why this number is adequate for answering the research questions:**

Sample: A non-probability sampling (convenience sampling) method will be adopted to allow reach all potential participants. The team members will approach potential respondents at Islamic centers to participate in this study. The inclusion criteria include women aged  $\geq 18$  years who speak English, self-identify as Muslim, and have not participated in our pilot study before. The exclusion criteria are any participants who participated in our pilot study or are unable to provide valid consent (e.g., developmental disability).

Qualitative analysis side: to develop the education material we will recruit 10 female participants above 18 years old who identify as Muslim to participate in the design of the religiously tailored and culturally appropriate education materials for the intervention. First the focus group will help select the targets of the proposed education and the content to achieve each target (design). As a next step the focus group will focus on the formatting of the material, including basic usability testing (refine). Based on information from these sessions we will finalize the educational material for our intervention.

we will use the grounded theory for complete the analysis

Statistical Analysis for quantitative side : We assume that our study's CC-S HPV-Vax uptake rate would increase by 10% post-intervention. Based on a power analysis assuming the use of the student T-test to assess the difference in outcome between the intervention and control groups. The target sample size is estimated based on the G power software sample size calculator for the minimal sample size needed for an unlimited population size using a confidence interval of 80%, a standard deviation of 0.5, and a margin of error of 5%. The study requires 10 participants for intervention to test the feasibility of the program.

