**See the help text for additional guidance**

**1. A statement explaining the study design**

**Study Design:**

The proposed study consists of two parts.

Part 1 involves formative research through a focus group to gather insights and reach saturation.

Part 2 is a single-arm pre and post-test trial with the objective of evaluating the efficacy of an educational interventional program.

The study aims to increase cervical cancer screening (CC-S) and HPV vaccine (HPV-Vax) rates among Muslim American women (MAW) in Virginia, leading to a reduction in cervical cancer (CC) incidence and mortality.

2. A detailed description of all the procedures that will be followed to carry out the study, preferably in sequential order, and in sufficient detail that the study's methods could be replicated.
  - a. Part 1 - Formative Research: Conduct a focus group with 10 participants until saturation is reached.
  - b. Part 2 - Single-arm Pre and Post-test Trial: Enroll 20 participants to evaluate the educational program's effectiveness.

Participants will complete a baseline survey to assess their knowledge, attitudes, CC-S and HPV-Vax practices, and predisposing factors.

The survey will cover topics such as CC knowledge, experiences of medical mistrust, discrimination, spiritual coping, and fatalism.

3. The schedule and frequency of when and how procedures will be conducted (e.g. in person, online, phone, paper, etc.)

All procedures will be conducted in person at the Islamic Centers, except for follow-up phone calls.

Recruitment will occur during regular Friday prayers and religious holidays.

Participants will receive a brochure explaining the study and be screened for eligibility by the Research Assistant (RA). Eligible participants will be given a telephone contact for enrollment at a more convenient time.

The consent process will involve verbal explanation, providing the consent form in English, and allowing participants to ask questions. Follow-up surveys and confirmations will be conducted via phone calls.

4. A description of all research measures/tests/interventions that will be used, including analyses/tests conducted on specimens/biological samples (if applicable)

**Power Analysis:** No power analysis for this study. A target sample size of 20 participants has been determined based on PhD committee, the purpose of the project is training for the STUDENT.

Measures: Validated scales and surveys will be used to measure

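### The intervention summary places the baseline survey after the education and refers to two groups, which contradicts the single-arm pre/post design; the sentence should be replaced

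*Combined protocol and SAP*

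**What the plan says.** **The sentence at issue.** Study Procedures, question 4, describes one intervention group of 20 women who attend a 1.5-hour session on one day. It then says: "All participants from both groups will be given the survey at month 0 (baseline) after the delivery of the educational material".

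**The design elsewhere.**
- Study Procedures, question 6, item 1: "Part 2 is a single-arm pre and post-test trial with the objective of evaluating the efficacy of an educational interventional program".
- H1 (Study Procedures, question 2): "Participants will show significant improvements in knowledge and acceptance of cervical cancer prevention after the intervention". For its test, Background, Rationale and Goals, question 2, says: "we will conduct a pre-post survey to examine changes in knowledge and acceptance of cervical cancer screening and prevention".
- Study Procedures, question 2, lists a pre-test survey and a post-test survey separately. The measures in question 6, item 4, refer four times to surveys before and after the intervention (age, education, uptake, feasibility). Compensation, question 1, pays $75 for each of the two surveys.
- Study Procedures, question 4, on eligibility: "For the one-arm clinical trial, participants will be screened for eligibility during the scheduling of baseline surveys". Question 6, item 2, requires a baseline survey but does not place it relative to the session.
- Study Procedures, question 6, item 3: "Follow-up surveys and confirmations will be conducted via phone calls". No date or window is given.

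**Event timetable.** Behavioral Intervention/Task Details, question 1, gives three hours: 90 minutes of education, one survey of 45 minutes, and the rest for a break and lunch.

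**Remaining two-group wording.** The closing summary of Background, question 1, speaks of "using a two-arms study design to improve the cervical cancer disparities among Muslim women". The sample-size answer (Study Population, question 3) assumes a t-test "to assess the difference in outcome between the intervention and control groups".

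**Primary outcome.** Background, question 3, and Study Procedures, question 2, name awareness of prevention methods. The outcomes text in Study Procedures, question 6, names the number of women who are screened.

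**The concern.** In a single-arm study the pre-test is the only comparator. A baseline taken after the education is already a post-intervention measurement, so a change from it would not be the change that H1 describes. A missed pre-test cannot be recovered later.

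The sentence also sits in operational text. The form answers that there is no separate protocol document, so this description is what staff would work from. Other places name a pre-survey, but no other supplied sentence says explicitly where the baseline survey falls relative to the education.

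A second, smaller question is when the post-test takes place and whether the phone follow-up surveys are that post-test.

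**Working it through.** The plan gives no figure of its own on this point, and no power or sample-size calculation bears on it. The check is a comparison of texts plus short arithmetic.

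**1. The sentence against the design**

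| Element | Intervention summary sentence | Rest of the form |
|---|---|---|
| Groups | Two | One arm, 20 women |
| Baseline survey | After the education | A pre-test, listed and paid for separately |
| Surveys | One | Pre-test and post-test |

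The last column leaves aside the two leftover two-group phrases noted above.

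**2. Could another reading rescue the sentence?**
- *A lost* and *before* after: one survey at baseline and one after the education. This restores the pre/post order, but the reference to two groups remains wrong for a single arm.
- *A mislabelled post-test*: the baseline survey is taken at a separately scheduled appointment, and the survey at the event is the post-test. This fits the eligibility text and the single survey in the timetable. The month 0 (baseline) label is then wrong.
- *A remnant of a two-group plan*: this fits the two-arm and control-group wording that survives elsewhere.
- *Both groups meaning focus group and trial*: the same answer later speaks of two phases in exactly that sense. But the focus group is not described as receiving the session, and this reading does not move the baseline ahead of the education.

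Under each reading the sentence still needs changing.

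**3. Literal reading (worst case)**
- Women with a pre-education value: 0 of 20.
- Scales that carry H1 and appear in both survey lists: cervical cancer knowledge, attitude about screening, HPV vaccination acceptability = 3. Change = post − pre, and pre is missing for all 3.
- Completion of the pre-intervention survey, part of the feasibility measure: 0 of 20. Enrollment and attendance stay measurable.

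**4. Event timetable**
- Time left = 180 − 90 − 45 × (surveys on the day).
- One survey: 180 − 90 − 45 = 45 minutes.
- Two surveys: 180 − 90 − 90 = 0 minutes.

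The event as timed holds one of the two surveys together with a break and lunch. That is not a contradiction in itself, since the other survey may be held on another occasion. But that occasion must be stated.

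**5. Post-test interval**
- If awareness is primary, a post-test on the day of the session can measure it.
- If screening is primary, uptake is self-reported, with items on whether a woman has ever had the test. Answers to such an item cannot change over one afternoon's event, so the interval decides whether the outcome can be observed.

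**The case against.** The strongest case against is that the intent is clear. A pre-test is listed as a separate instrument, paid for, scheduled and mentioned repeatedly, so staff would have to ignore all of this to omit it. A reader might infer from the sentence that the trial has no pre-test, or that its efficacy comparison is already lost. The documents do not support that. The figure of 0 of 20 is a worst case under a literal reading, not an expected result. What stands is that the one explicit instruction on order is wrong as written.

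A reader might also infer that a control group is planned. The current design text says single arm in several places, and the two-group phrases look like leftovers.

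A third tempting inference is that the undated post-test undermines the trial however the sentence is read. It does not. With the lost *and* restored, or with the survey read as a mislabelled post-test, the post-test is anchored after the session and only the interval is missing. Awareness, which two sections name as primary, can be measured the same day.

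Finally, the uploaded timeline, session guide, communication script, survey and consent files are not in the supplied text and may state the timing. The point about the interval is therefore limited to what was supplied. Even if those files give the right order, the sentence would still contradict them and need correcting.

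**Conclusion.** The sentence contradicts the single-arm pre/post design on both the number of groups and the order of survey and education. It should be corrected before enrollment. It is most likely a drafting error. Its possible cost is the loss of the only comparator for H1 in all 20 women, if staff follow it literally.

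The missing post-test interval and the undefined role of the phone follow-up are secondary. They affect conclusions only if screening uptake is the primary outcome. If awareness is primary, they are missing detail. The same holds for the time at which retention above 80% (at least 17 of 20, since 16/20 is exactly 80%) is counted.

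This rests on the supplied text alone and on the reading that one arm of 20 is the intended design.

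**What to change.** 1. Replace the sentence in Study Procedures, question 4, with: *All 20 participants complete the pre-test after consent and before any education content, and the post-test after the session.* Delete the reference to both groups.
2. Align the timetable in Behavioral Intervention/Task Details, question 1, with the chosen pre-test occasion.
3. State the post-test interval and say whether the phone follow-up surveys are the post-test.
4. Reconcile the two statements of the primary outcome. If the post-test is on the day of the session, state that it supports change in knowledge, attitude and acceptability, but not screening or vaccination uptake.

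**Cost.** The wording changes are small, and the pre-test payment is already planned (20 × $75 = $1,500).
- *Both surveys on the event day, with the 45-minute break kept (an assumption):* 90 + 45 + 45 + 45 = 225 minutes instead of 180, plus the satisfaction survey if it is also held then. Its length is not stated.
- *Pre-test at an earlier appointment:* 20 × 45 = 900 minutes, or 15 participant-hours, move to another day. Consent must then be taken before that appointment. The intervention consent answer (Consent Groups, question 7), which places consent at the education sessions and describes a one-day program, would need revising.
- *A later contact for uptake added to a same-day post-test:* Compensation lists payments only for the pre-, post- and satisfaction surveys in the intervention part, so this contact has no payment yet.
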